*** 4. Will there be any follow-up or will reminders be sent?**

Yes

*** 4.a. Please explain.**

Email and phone calls will be used to update patients.

*** 5. Differentiate any procedure being done solely for research purposes from procedures being done anyway.**

Not applicable.

*** 6. Describe the time you have available to conduct and complete the research (ex. the time from initiation of the research to completion of data analysis).**

Sufficient time will be allotted to complete this project. If sufficient subjects are not initially available, we will use a rolling enrollment to obtain the number of subjects required.

Recruiting Procedures

*** 1. How will the names and contact information for participants be obtained?**

Personal interview, email, or phone conversation.

*** 2. How will participants be approached about participating in the study?**

Paper and online advertisements.

Benefits and Risks

*** 3. Explain the benefits to participants or to others.**

The study is designed to have participants meet the recommended intakes of fruits and vegetables and whole grains during the intervention periods. Any benefits arising from meeting the USDAs recommended servings of these foods may be realized in this study.

You will also receive a copy of your dietary analysis along with the findings from the blood tests at the end of the study. This will show intake of nutrients and food groups. You can also request the findings from your blood tests, which include fasting blood glucose, cholesterol, LDL cholesterol (bad cholesterol), HDL cholesterol (good cholesterol), triglycerides, and the inflammatory markers IL-6, C-reactive protein, and lipopolysaccharide binding protein. These results of the tests and analysis should be interpreted by your primary care physician.

Benefits to others include new evidence in support of whole wheat in the diet for prevention of inflammation and reduction of risk factors of many of the very diseases that have been implicated in wheat-based diets. This project could lead to improved understanding of how whole wheat mediates an anti-inflammatory effect, allowing health professionals to offer better suggestions to individuals on how to make the most positive impact on health through diet. Due to the rising problems associated with consumer health, this project has the potential to have a positive impact on the well-being of many individuals.

*** 4. Explain the risks to participants. What will be done to minimize the risks? If there are no known risks, this should be stated.**

Participants may experience gastrointestinal discomfort from consuming fruits and vegetables or whole grains if they are not used to consuming these products normally. This will be monitored through gastrointestinal symptom diaries that will be filled out by participants. Typically, the discomfort subsides within days. If discomfort persists for longer than this the individual will be invited to withdraw, but given the option to remain in the study.

Participants may also experience some discomfort during blood draw. Additional risks during blood draw include bruising, infection, and dizziness. Standard procedures will be used to minimize discomfort. Participants will be well-informed that this will be required for inclusion in the study.

Participants may experience some embarrassment when providing a stool sample. Stools will be collected privately by the participant using a stool collection kit that fits on the toilet seat. This kit contains a removable opaque container with a lid, so the specimen can be transported discretely.

If the participants are concerned about any physical distress they are experiencing during the study, they will be referred to their medical provider.

*** 5. Describe the availability of medical or psychological resources that participants might require as a consequence of the research.**

None.

Compensation

*** 6. Will compensation (including money, gift certificates, extra credit, etc.) be provided to participants?**

Yes

*** 6.a. Please describe the amount and type of compensation.**

During screening, subjects will complete a diet history questionnaire. They will receive \$5 for completing this questionnaire. Of the subjects enrolled in the study, if a participant begins the study but withdraws, they will receive \$20. Upon completion of the study, subjects will receive \$75. When subjects receive payment of \$75, a research participant disclosure form with social security number will be collected. If compensation is \$5 or \$20 no social security number will be collected. Receipts from compensation will be kept in a locked drawer during the study and then returned to the bursar's office for storage for 7 years as required by law.

Subjects will not be required to purchase test foods. These will be provided by the study personnel. Other foods consumed during the study period will be purchase by the subjects.

Informed Consent Process

*** 1. How will informed consent/assent be obtained?**

Paper signature following a personal meeting/interview with study personnel.

*** 2. Who will conduct the consent interview?**

Study personnel

*** 3. Who will provide consent or permission?**

The subject.

*** 4. What is the waiting period, if any, between informing the prospective participant and obtaining consent?**

There is no waiting period.

*** 5. What steps will be taken to minimize the possibility of coercion or undue influence?**

If participants are given a oral invitation to participate, this will only be done once.

*** 6. What is the spoken language used by those obtaining consent?**

English

*** 7. What is the language understood by the prospective participant or the legally authorized representative?**

English

*** 8. Will any subjects be decisionally impaired so that they may not have the capacity to give consent?**

No

*** 9. In certain cases for children over the age of 14, such as UNL students who are 17 or 18, waivers of informed consent can be granted. Would you like to request a waiver of consent?**

No

Confidentiality

*** 1. The research plan should make adequate provisions to maintain the confidentiality of the data. How will confidentiality of records be maintained?**

Subjects will receive a 3 digit code number at the beginning of the study and will be identified by this number throughout the study. This code will be used to identify sample both in the online data (diet history questionnaire) and the biological sample data. Only 1 file will contain the names and contact information of individuals with corresponding code number. This will be maintained by one of the study personnel on a computer that is property of the University and has a single user. The computer log-in as well as the file containing names will be password protected.

*** 2. Will individuals be identified during data collection or in the results?**

Yes

*** 2.a. Will the participants be identifiable during data collection? How long will individuals be identifiable? At what point will the identities be removed (if ever)?**

Participants will only be identifiable in one key file containing personal information for contact purposes. This file will be password protected and kept on a computer with a single user that is also password protected. All other files will only contain the participant's ID number. Once data collection and verification is complete, the file with names and personal information will be destroyed.

*** 2.b. If the data is coded, will there be a list linking names and codes? If so, how long will this list be kept and where?**

The file linking names with codes will be kept on a private computer maintained by one of the study personnel for a period of 5 years.

*** 3. How long will records be kept?**

5 years.

*** 4. Where will records be stored?**

In locked offices on private computers.

*** 5. Who has access to the records/data?**

The project director and the graduate student on the project. Collaborators will only have access to coded data (not containing names or contact information).

*** 6. How will data be reported (e.g., in a dissertation or thesis, in scientific journals, at conferences, etc)?**

Dissertation, conferences, and in scientific journals. Data will be reported in a summarized format (not individually).

Data Monitoring

* 7. Does this research involve more than minimal risk to participants?

No

Questionnaires, Surveys, and Testing Instruments

* Please list all questionnaires, surveys, and/or assessment instruments/measures used in the project.

Diet history questionnaire (online; a demo can be found here: <http://appliedresearch.cancer.gov/dhq2/webquest/demos.html>)

Uploaded Attachments

Please submit copies of the following:

- Funding application
- Institutional Approval letters
- Recruitment flyers, ads, phone scripts, emails, etc.
- Informed Consent Forms, emails, and/or letters
- If transcriptions are required, Confidentiality Agreement that transcriptionists will sign
- If this is a study utilizing PHI, Release of Authorization that will be used to obtain permission from the participant for the agency/institution to release protected health information for project purposes or a letter from the agency/institution documenting agreement to provide protected health information for project purposes
- All Instruments/Measures used in the project

Please upload all documents that would include the IRB approval stamp as a PDF. These documents could include recruitment materials AND informed consent/assent forms.

- Wheat proposal v4.pdf
- Approval letter.pdf
- Instructions for completing diet history questionnaire.pdf
- Project amendment and approval.pdf
- dhq2_pastmonth.pdf
- Food diary.pdf
- GI symptom diary.pdf
- Participant contact script.pdf
- Participant reminder.pdf
- Compensation document less than 50 dollars.pdf
- Compensation document more than 50 dollars.pdf
- Informed Consent Form.pdf
- Participant enrollment script.pdf
- Recruitment flier.pdf

**NCT02602496**

## **Statistical analysis**

Power. We estimated that we would be able to detect an effect size of 0.4 with 80% power by recruiting 52 subjects total divided into 3 groups. This was based on our whole grain barley and brown rice feeding trial in overweight subjects, where we saw an effect size of 0.48 for change in IL-6 with the whole grain treatment.

Analyses after the intervention. All data with the exception of OTU comparisons will be analyzed using SAS software (version 9.4, SAS Institute, Cary, NC, USA). Differences across treatment groups will be assessed using ANOVA where treatment group was the main factor and BMI (at baseline), gender, and baseline measurement were covariates. Changes in measured variables from baseline to the end of the study within each group will also be assessed after correcting for BMI (at baseline), gender, and baseline values. Stool bacterial data will be log2 transformed for the statistics and then converted back to the numerical values for data presentation. Correlations will be analyzed using Pearson's method. Changes in OTU abundances will be determined using DESeq2 (ver. 1.14) [33] in the R Bioconductor package (<http://www.bioconductor.org>) (ver. 3.1.2). P-values for stool bacterial data and correlations will be corrected using the false discovery rate procedure. P-values for other comparisons will be adjusted using Tukey's procedure. Adjusted  $p < 0.05$  will be considered significant.

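### FDR control of the Pearson correlations is not held when both variables in a pair are skewed or sparse; the SAP log-transforms only the bacterial data

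*SAP*

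**What the plan says.** All of the relevant text is in the SAP, section Statistical analysis, paragraph on analyses after the intervention.

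- Method: "Correlations will be analyzed using Pearson's method".
- Multiplicity: "P-values for stool bacterial data and correlations will be corrected using the false discovery rate procedure". The FDR variant is not named.
- Threshold: an adjusted p below 0.05 "will be considered significant".
- Scale: stool bacterial data are put on a log2 scale, "transformed for the statistics and then converted back to the numerical values for data presentation". No other variable is given a transformation.

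The Protocol (Benefits and Risks, item 3) lists the blood results: glucose, lipids and "the inflammatory markers IL-6, C-reactive protein, and lipopolysaccharide binding protein". Neither document says which variables are correlated, how many correlations there are, whether levels or changes are used, how zeros in the bacterial data are treated, or how rare a taxon may be and still be included. There is no rank-based or permutation alternative.

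**The concern.** Pearson's p-value comes from a t distribution that is exact when at least one of the two variables is normal. When both are skewed, or one is mostly zeros and the other is skewed, one or two subjects can carry the whole coefficient. The rejection rate at p < 0.05 hardly moves, so a routine check would not reveal the problem. The excess lies far out in the tail, and an FDR step over many correlations works in that tail.

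At stake is the reading of the exploratory links. The Protocol (Research Purpose of Project, item 1) hypothesises that an anti-inflammatory microbial metabolite contributes to the benefit of whole grains. The SAP names no analysis other than correlation that could tie bacteria to blood markers. That correlations will carry this claim is an inference; the documents do not say so.

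**Working it through.** **Inputs from the documents.** Pearson; FDR; adjusted p < 0.05; log2 for bacteria only; 52 subjects (SAP). The Protocol's Description of Participants gives 100 (item 1) and 120 (item 5). The SAP figure is used here.

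**Assumptions, because the documents are silent.** Two-sided tests; Benjamini-Hochberg as the FDR procedure; skewed variables lognormal; variables independent; number of correlations m from 10 to 400.

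**The plan's own figure.** The only related number is the sample size: the SAP says "we would be able to detect an effect size of 0.4 with 80% power" "by recruiting 52 subjects total divided into 3 groups". A two-sided paired t-test with d = 0.4 gives 52 (power 0.808), and a 1-df contrast with f = 0.4 also gives 52 (power 0.807). A three-group omnibus F-test with f = 0.4 needs 64 and has power 0.71 at 52. That is a separate matter; here 52 serves only as n.

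**Step 1: where FDR acts.** The test is t = r·√[(n − 2)/(1 − r²)] on n − 2 = 50 df. Benjamini-Hochberg declares something significant if any ordered p-value satisfies p(i) ≤ 0.05·i/m. For m = 8 × 8 = 64, the smallest p-value must reach 0.05/64 = 0.00078, or |r| of about 0.45. An unadjusted p = 0.05 needs only |r| of about 0.27.

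**Step 2: Pearson's tail with two unrelated lognormal variables, n = 52.** The rate at p < 0.05 is 4.9%. At p < 0.001 (nominal 0.1%) it is 0.29%, 0.55% and 0.90% for log-SD 0.6, 0.8 and 1.0.

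**Step 3: hand check.** The chance that at least one of 64 independent tests falls below 0.001 is 1 − (1 − q)^64:

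- q = 0.001: 6%
- q = 0.0029: 17%
- q = 0.0055: 30%
- q = 0.0090: 44%

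The 0.001 cut is slightly looser than 0.00078, so these should sit a little above the full simulation.

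**Step 4: simulation with the FDR step, all true correlations zero.** Chance of at least one FDR-significant result for 64 pairs, with ranges across repeat runs:

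| log-SD of both variables | Pearson | Spearman |
|---|---|---|
| 0.4 | 7% | about 6% |
| 0.6 | 12-15% | 5-6% |
| 0.8 | 27-29% | 5-6% |
| 1.0 | 41-42% | 5-6% |

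The rate depends strongly on m. At log-SD 0.75 it is 9%, 17%, 31% and 54% for m = 10, 30, 100 and 400. Intercorrelation lowers it: at log-SD 1.0 and m = 100, a correlation of 0.5 within each set reduces 52% to 28%.

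**Step 5: bacteria with markers, respecting the log2 step.** The model has 50 log2 taxa (zero when absent) against 8 raw lognormal markers.

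- Detection 10-100% of subjects: about 8-20%.
- Detection 30-100%: about 4-6%.
- Taxa normal on the log2 scale against a skewed marker change: 4-6%.

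So with levels, the inflation comes from taxa found in fewer than about 30% of subjects. That boundary depends on the model. If changes are correlated and the marker change is left raw (log-SD 0.75), a taxon at 50% prevalence still gives 10%, 12%, 18% and 28% for m = 10, 30, 100 and 400.

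**Step 6: do the remedies work?** Markers logged, sparse log2 taxa kept: 4-5%. Permutation p-values at m = 30 (500 trials): 3.8% for lognormal pairs and 6.2% for sparse taxon change with skewed marker change. Spearman with large-sample p-values fails for pairs of taxa both at 10% prevalence: 27%, 45% and 75% for m = 30, 100 and 400.

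**The case against.** The strongest reply is that the SAP already protects the correlations of most interest. Bacterial data are logged, and Pearson needs only one near-normal member per pair. For commonly detected taxa it holds about 5% even against a raw, strongly skewed marker, and Spearman gains nothing there (about 5.5-7%). The SAP does not say that rare taxa enter the correlations, and OTU changes are tested separately with DESeq2. The blocks of skewed-by-skewed pairs are assumed too, as are their number, their skewness and their independence. All of this stands. It limits the point to pairs in which neither variable is near normal.

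A reader might infer that false FDR-significant correlations will appear in 15-27% of such trials, or that the FDR guarantee on the bacteria-inflammation links fails in general. The documents support neither. Those percentages are one slice of assumed settings; other settings run from about 5% to over 90%. They also assume that no true correlation exists, since only then does the chance of any false positive equal the FDR.

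What the reply leaves standing is that the SAP has no safeguard for the remaining pairs: marker with marker, marker with intake, and rare taxon with skewed marker. Logging the bacteria does not remove zeros and does nothing for the other variables.

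**Conclusion.** The point holds in a conditional form. As written, FDR at 5% is not held for correlations in which both variables are skewed or sparse. The size is illustrative: for 64 independent lognormal pairs at n = 52, about 7% at log-SD 0.4 rising to 42% at 1.0, and about 8-20% for 50 log2 taxa of mixed prevalence against 8 skewed markers. Where either variable is near normal, the plan is sound as it stands. The true size in this trial cannot be derived from the documents, because the pairs, their number, the skewness and the prevalence of the taxa are not given. This is a cheap improvement to a secondary analysis; it does not touch the comparison of treatment groups.

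**What to change.** Add to the SAP:

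1. The pairs to be correlated, their number, and whether levels or changes are used.
2. For skewed positive markers, a log transformation before Pearson (for changes, the difference of the logs). Where logging does not suit the variable, Spearman.
3. Permutation p-values entering the same FDR step. The smallest attainable value is 1/(B + 1) with B permutations, and it must not exceed 0.05/m, so B ≥ 20m − 1: at least 1,279 for 64 correlations and 7,999 for 400.
4. A prevalence cut-off, fixed before the data are seen, below which taxa are left out of the correlations, and a rule for zeros. This is needed even with Spearman, whose large-sample p-values fail for pairs of very sparse taxa.

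The cost is a few lines in the SAP and in the code. Spearman loses a little power where a pair really is normal and linearly related; logging the markers and keeping Pearson avoids most of that. Correlations involving rare taxa are given up.

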Subjects will be required to visit the clinical facility 2 times (weeks 0 and 4). At the clinical facility visit, subjects will be fasted (12 h fast) and a blood sample will be taken by a licensed phlebotomist using standard venipuncture techniques. Weight and height will be recorded. Subjects will give their stool sample to the study personnel either already collected or collected at the facility. If the subjects is unable to defecate at either of these times, they will be instructed to contact the study personnel as soon as possible after the visit to have the stool sample picked up.

The food diary requires writing down all of the fruits, vegetables, and whole grain products consumed everyday. There is a form supplied to help with this. For fruits and vegetables, subjects should write down the form (whole, peeled, juice, cooked, raw, etc.) that they were consumed in addition to the amount. For whole grains, subjects should write down the type of food and brand as well as the amount consumed.

*** 3. How long will these procedures take the participants to complete? Please describe the duration of the session, the number of sessions, over what period of time, etc.**

The blood and stool collection will take 20-30 min each session. The diet history record takes about 1 hour to complete. Each subject will complete these sessions at the beginning and the end of the study. During the study, subjects will be required to incorporate 3 servings of whole grain per day; 5 servings of fruits and vegetables per day; or noting (control) into their normal diets. This will take minimal extra time.

Total estimated time for participation in this study is 6 hours over the course of 5 weeks (six 20 minute study facility visits; two 30 minute clinical facility visits; two 60 minute diet history questionnaires; 60 minutes cumulative time filling out dietary records and GI symptom questionnaires).

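### Single-step Tukey is valid here, but with exactly three arms the closed (step-down) form rejects everything it rejects and sometimes more, at the same 5% family-wise error per variable

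*SAP*

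**What the plan says.** The SAP (Statistical analysis) compares groups by "ANOVA where treatment group was the main factor and BMI (at baseline), gender, and baseline measurement were covariates". On multiplicity it splits the results in two. First, "P-values for stool bacterial data and correlations will be corrected using the false discovery rate procedure". For everything else, "P-values for other comparisons will be adjusted using Tukey" (the sentence goes on to name the procedure), and an adjusted p below 0.05 "will be considered significant". No step-down or closed version is mentioned, so the plain reading is single-step Tukey. Simultaneous confidence intervals are not mentioned either.

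The arms are set out in the protocol (Methods and Procedures): participants add "3 servings of whole grain per day; 5 servings of fruits and vegetables per day; or noting (control) into their normal diets". That gives three pairwise comparisons. The SAP sizes the trial "by recruiting 52 subjects total divided into 3 groups".

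**The concern.** Single-step Tukey applies one enlarged critical value to all three pairs. With three arms this is more than family-wise control of the tests requires. If any two of the three pairwise equalities are true, all three means are equal. So once the overall hypothesis of equality has been rejected by Tukey's range test, at most one pairwise equality can still be true, and testing it at an unadjusted 5% cannot push the family-wise error above 5%.

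Keeping the larger critical value costs power for the second and third comparisons. At about 17 subjects per arm, power is scarce. What single-step Tukey offers in return is matching simultaneous intervals, which the SAP does not plan, and a lower error for a truly equal pair when the third arm differs.

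**Working it through.** **Inputs.** From the SAP: 52 subjects, 3 groups, 3 covariates, adjusted p < 0.05. Assumed: arms of 17/17/18 (52/3 = 17.3), two-sided tests, and standard errors set by arm size alone, with no covariate imbalance. Error df = 52 − 3 − 3 = 46.

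**The plan's own power figure.** The SAP claims to "detect an effect size of 0.4 with 80% power" with 52 subjects. Read as Cohen's f = 0.4, this reproduces for a test with one numerator df (power 0.807) but not for the three-group F-test (power 0.707). It also reproduces for a paired t-test at d = 0.4 on all 52 as one group (0.808). The type of effect size is not stated, so a range of differences is shown below.

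**Critical values.**
- Single-step Tukey, every pair: |t| > q(0.95; 3, 46)/√2 = 2.42, a nominal two-sided p of 0.019.
- Closed form: at least one pair must pass 2.42; after that, each remaining pair needs |t| > t(0.975; 46) = 2.01.

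**No Tukey rejection is lost.** The closed adjusted p for a pair is max(its unadjusted p, the smallest of the three Tukey p-values). Neither term can exceed that pair's own Tukey p, so the maximum cannot. This is algebra and needs no assumed effect. The pair with the smallest Tukey p is rejected under both methods or under neither, so the chance of at least one rejection is identical.

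**Error control per variable.**
- All means equal: a false rejection requires the smallest Tukey p to be below 0.05, the same event under both methods (simulated 5.0% for each).
- Exactly one pair equal: a false rejection requires that pair's own t-test to reject, so at most 5%. With the third arm far away, simulation gives 5.0% closed against 1.9% Tukey.

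**Power, both diets equally far from control** (simulated, Tukey → closed):

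| Difference (residual SD) | Power per diet | Power for both diets |
|---|---|---|
| 0.4 | 11-12% → 14% | 4% → 8% |
| 0.48 | 17% → 20% | 7% → 13% |
| 0.8 | 47-48% → 54-55% | 32% → 45% |
| 0.849 (arms 18/17/17) | 54% → 61% | 38% → 52% |
| 1.0 | 69-70% → 76-77% | 56% → 70% |

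The 0.849 row is f = 0.4 with one arm apart from the other two: f = d√2/3, so d = 0.4 × 3/√2 = 0.849. No simulated trial had a Tukey rejection that the closed form missed.

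**With 120 subjects.** The protocol (Inclusion Criteria, item 5) gives 120, about 40 per arm. At 0.849 SD, power per diet goes from 92.0% to 95.3%, a gain of 3.3 points against about 7 at 52 subjects. At 0.4 SD it goes from 28.3% to 33.0%, a gain of 4.7 points against about 2. So the gain is smaller at large differences, but not at every difference.

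**The case against.** The strongest reply is that nothing is broken. Tukey is a valid, pre-stated adjustment, and choosing among valid procedures is partly preference. This stands: the point is about efficiency, not validity. A reader might infer that the planned analysis is wrong, or that the trial loses its chance of a finding. The documents support neither, since family-wise error is controlled for each variable and the chance of at least one rejection is the same.

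A reader might also infer that single-step Tukey buys nothing for testing. That goes too far. When two arms are truly equal and the third differs, Tukey's error for the equal pair is about 2%, while the closed form lets it rise to as much as 5%. This is within the nominal level, but it is a real trade. It recurs on each of the eight blood measures listed in the protocol (Benefits and Risks, item 3), because neither method adjusts across variables.

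The size of the gain is also open to challenge. The SAP's source figure is "we saw an effect size of 0.48 for change in IL-6 with the whole grain treatment". If 0.4 and 0.48 are mean differences in SD units, the gain is only 2-3 points per diet. The larger gains need differences of about 0.8 SD or more, which fits if 0.4 is Cohen's f. Power to show both diets differ is illustrative, because neither document names required contrasts or makes both a criterion of success.

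Finally, the step-down form does not repair the sample-size statement, and it does not settle which N applies: the SAP says 52, while the protocol says 120 in one place and 100 in another (participant chart).

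**Conclusion.** The point holds as an optional improvement. For three arms, closed Tukey is never worse than single-step Tukey in what it rejects and has the same 5% family-wise bound per variable. That part rests on algebra.

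The size depends on assumptions: equal allocation of 52, two-sided tests, 46 error df, and two diets equally far from control. On these, the gain runs from 2-3 points per diet at 0.4-0.48 SD to about 7 points at 0.8-1.0 SD. For showing both diets, it runs from about 4 points to about 14.

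The result is specific to three arms and to one variable at a time. It also requires Tukey's range test as the first step. An ANOVA F-test as the gate would also control the error, but it would occasionally miss a pair that Tukey rejects (about 0.1% to 1.6% of simulated trials), so the statement that nothing is lost would fail.

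**What to change.** For the between-group pairwise comparisons only, state in the SAP:

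> For each variable, the adjusted p-value for a pair is the larger of its unadjusted two-sided p and the smallest of the three Tukey-adjusted p-values; adjusted p < 0.05 is significant.

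Two details of the wording matter.

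- The rule should use the smallest Tukey p, not the largest difference in means. The two can disagree when standard errors differ. Gating on the largest difference would then discard a pair that Tukey rejects, in about 0.01% of trials at 17/17/18 and up to about 0.8% at an assumed 22/18/12 split.
- The SAP also tests changes within each group, and its Tukey sentence may be meant to cover them. The new sentence must not replace any adjustment of those tests, which stays as it is.

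The cost is one sentence and no extra subjects. There are two downsides. The error for a truly equal pair rises from about 2% to at most 5% when the third arm differs. And if Tukey intervals are shown, the interval for a second-step pair can include zero although its adjusted p is below 0.05; a footnote should say so.
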